Abbreviations: α -Syn: α -synuclein; β -HCG: beta-human chorionic gonadotropin; AE: adverse event; BDI-II: Beck Depression Inventory, second edition; CGI: Clinical Global Impression; CSF: cerebrospinal fluid; DAT: dopamine transporters; DAT scan, ioflupane I-123 injection DaTSCAN; DBS: dried blood spot; ECG: electrocardiogram; EQ-5D: EuroQol Five Dimensions questionnaire; FES: Falls Efficacy Scale; GBA: glucocerebrosidase gene; GCase: glucocerebrosidase; GL-1: glucosylceramide; H&Y: Hoehn and Yahr; HRPQ: Health-Related Productivity Questionnaire; IMP: investigational medicinal product; LP: lumbar puncture; lyso-GL 1: glucosylsphingosine; MDS-UPDRS: Movement Disorder Society-Unified Parkinson's Disease Rating Scale; MoCA: Montreal Cognitive Assessment; MRI: magnetic resonance imaging; NFL: neurofilament light chain; PD: Parkinson's disease; PD-CRS: Parkinson's Disease-Cognitive Rating Scale; PDQ-39: Parkinson's Disease Questionnaire - 39; PGIC: Patient Global Impression of Change; PK: pharmacokinetics; qd, daily; RBD: rapid eye movement sleep behavior disorder; SDMT: Symbol Digit Modalities Test; TMT-A: Trail Making test A; TMT-B: Trail Making test B; WOCBP: women of childbearing potential.

- a For patients who have previously completed Part 1, the following will NOT have to be repeated: GBA mutation and LRRK2 screening, GCase: dried blood spot, MRI, LP, and DAT scan.
- b This visit will serve as the screening for patients enrolling into Period 3.
- c Genetic screening will not need to be repeated to confirm eligibility of patients from Part 1 to enroll in Part 2. Once the results of the GBA gene sequencing (positive for a GBA mutation) and the LRRK2 genotyping (negative for the G2019S mutation) are confirmed, the remaining of the screening activities can continue.
- d Confirmed by historically documented polysomnography or by RBD screening questionnaire.
- e Once patients demonstrate eligibility based on screening criteria, MRI, LP, and DAT scan will be performed, except for the patients who completed these baseline assessments in Part 1. Baseline MRI must be done at least 7 days prior to the end of the screening period (Day -8). DAT scans will be performed only in countries where it is approved.

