1.3.3 Part 2: Study schedule of assessments (Periods 3 and 4)

Study Period	Long-Term Follow-up Period (Period 3)												8-Week Follow-up Visit (Period 4)
	W65 ^f (±7 days)	W78 ^f (±7 days)	W91 ^f (±7 days)	W104 (2 years) ^f (±7 days)	W117 ^f (±7 days)	W130 ^f (±7 days)	W143 ^f (±7 days)	W156 ^f (3 years) (±7 days)	W169 ^f (±7 days)	W182 ^f (±7 days)	W195 ^f (±7 days)	W208 ^f (4 years) (±7 days)	
Visit number	9.1 (for Japanese patients only)	10	10.1 (for Japanese patients only)	11	11.1 (for Japanese patients only)	12	12.1 (for Japanese patients only)	13	13.1 (for Japanese patients only)	14	14.1 (for Japanese patients only)	15	16
Visit at clinical site	X	X	X	X	X	X	X	X	X	X	X	X	X
Concomitant medications	X	X	X	X	X	X	X	X	X	X	X	X	X
Study treatment administration													
GZ/SAR402671	qd												
Dispense IMP		X		X		X		X		X			
Dispense/check patient diary		X		X		X		X		X		X ^b	X ^b
Biomarkers^c													
Biomarkers: serum and plasma				X				X				X	
Safety													
Physical examination				X				X				X	X

Study Period	Long-Term Follow-up Period (Period 3)												8-Week Follow-up Visit (Period 4)
	W65 ^f (±7 days)	W78 ^f (±7 days)	W91 ^f (±7 days)	W104 (2 years) ^f (±7 days)	W117 ^f (±7 days)	W130 ^f (±7 days)	W143 ^f (±7 days)	W156 ^f (3 years) (±7 days)	W169 ^f (±7 days)	W182 ^f (±7 days)	W195 ^f (±7 days)	W208 ^f (4 years) (±7 days)	
Visit number	9.1 (for Japanese patients only)	10	10.1 (for Japanese patients only)	11	11.1 (for Japanese patients only)	12	12.1 (for Japanese patients only)	13	13.1 (for Japanese patients only)	14	14.1 (for Japanese patients only)	15	16
Neurological examination		X		X		X		X		X		X	X
Vital signs, body temperature	X	X	X	X	X	X	X	X	X	X	X	X	X
Body weight				X				X				X	
Hematology				X				X				X	
Biochemistry, urinalysis				X				X				X	
Urine pregnancy test (for WOCBP)		X		X		X		X		X		X	
Ophthalmology examination ^d		X		X		X		X		X		X	X
12-lead ECG				X				X				X	
Adverse event collection	X	X	X	X	X	X	X	X	X	X	X	X	X
Assessments^e													
DAT scan				X				X				X	

Study Period	Long-Term Follow-up Period (Period 3)												8-Week Follow-up Visit (Period 4)
	Day (D) or Week (W) (allowed range)	W65 ^f (±7 days)	W78 ^f (±7 days)	W91 ^f (±7 days)	W104 (2 years) ^f (±7 days)	W117 ^f (±7 days)	W130 ^f (±7 days)	W143 ^f (±7 days)	W156 ^f (3 years) (±7 days)	W169 ^f (±7 days)	W182 ^f (±7 days)	W195 ^f (±7 days)	

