4.2.2 Risk assessment

GZ/SAR402671 has not been studied in patients with GBA-PD. In the completed Phase 1 clinical trials in healthy volunteers, oral administration of GZ/SAR402671 was safe and generally well tolerated.

Based on toxicology data, the target tissues identified in rats were the lens, germinal epithelium of the testes, gastrointestinal tract, and the liver. Further analysis of data indicates that there seems to be no safety concern in humans involving the gastrointestinal tract and the liver.

In a juvenile toxicology study in rats given GZ/SAR402671, unilateral/bilateral degeneration of germinal epithelium in the testes of males and lenticular (eye lenses) degeneration in both sexes were observed. Lens swelling was also reported in adult female rats given a high dose of 20 mg/kg but no lens findings were observed in dog studies. Adult rodent and dog study data indicate no anticipated impact on adult male GBA-PD patient fertility. Additional information is provided in the GZ/SAR402671 Investigator's Brochure (IB).

As a result of rodent lens findings, GBA-PD patients with cataracts (excluding those with nuclear cataracts) are excluded from ACT14820. Furthermore, patients currently receiving potentially cataractogenic medications as listed in [Section 7.2](#) are excluded. The effect of GZ/SAR402671 on the lens will be closely monitored throughout the clinical trial through periodic ophthalmology examinations as detailed in [Section 9.3.3.6](#). Additionally, there is a theoretical risk of CNS effects given the compound's access through the blood-brain barrier to the CNS. However, preclinical studies in rats did not suggest the occurrence of untoward effects on the CNS at the no observed adverse effect level of 45 mg/kg/day (approximately 10-fold the above expected clinical exposure).

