6.5 DISCUSSION OF STUDY DESIGN

Current treatment options for PD patients, with or without GBA mutations, are limited due to side effects. Despite the many therapeutic agents available for the treatment of PD, patients can still experience intolerable disability due to disease progression. Thus, there is a high unmet medical need for better treatment alternatives in PD. Participation in this placebo-controlled study, with a novel mechanism of action, would present a unique opportunity for the patients. Patients will be allowed to start on PD therapy (only an immediate release levodopa formulation is allowed) or to continue to take their medication as usual (if already taking PD medication at study start).

Of note, PD prescription medications permitted (see [Section 8.8](#)) in this trial include:

- Dopamine replacement therapies (eg; levodopa/carbidopa).
- Dopamine agonists (eg; pramipexole, ropinirole, bromocriptine).
- Monoamine oxidase B inhibitors (eg; rasagiline).
- Catechol-O-methyltransferase inhibitors (eg; entacapone, tolcapone).
- Anticholinergics (eg; artane, cogentin).

The following points were taken into consideration in the design of the study:

- **Screening:** Sequencing of the GBA gene and genotyping for a LRRK2 (G2019S) mutation to ensure patient eligibility will be conducted from a collected whole blood sample even if historical results are available.
- **Randomization (Day 1, pre-dose):** To reduce the risk of imbalance between treatment groups with respect to cognitive function and PD medication. In Part 2, randomization will be stratified based on use of levodopa/PD medication (yes/no), cognitive function (MoCA score <26 [yes/no]) and severe GBA mutation (yes/no).
- **Long-term follow-up (Part 2):** Upon completion of the 52-week treatment period, eligible patients will be followed in an LTFU period for 36 months. Patients in the placebo arm will be switched to GZ/SAR402671 treatment after completing the Week 52 study visit. During the LTFU period, study drug assignment will remain blinded and patients will continue to be assessed by a blinded rater, thus collecting important information and

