7.2.3 Exclusion criteria related to current knowledge of GZ/SAR402671 IMP

- E 22. Liver enzymes (alanine aminotransferase [ALT]/aspartate aminotransferase [AST]) or total bilirubin >2 times the upper limit of normal (ULN) at the time of screening. Patients with Gilbert's disease are excluded only from Part 1 participation.
- E 23. Renal insufficiency as defined by creatinine >1.5 times ULN at the screening visit.

- E 24. The patient has a documented diagnosis, as per local regulations, of any of the following infections: hepatitis B, hepatitis C, human immunodeficiency virus 1 or 2.
- E 25. The patient has received strong or moderate inducers or inhibitors of CYP3A4 (see [Section 17 \[Appendix E\]](#)) within 30 days or 5 half-lives of these medications, prior to randomization, whichever is longer.
- E 26. Use of the following medications within 5-elimination half-lives prior to the DAT neuroimaging evaluation: amoxapine, amphetamine, benztropine, bupropion, buspirone, cocaine, mazindol, methamphetamine, methylphenidate, norepinephrine, phentermine, phenylpropanolamine, selegiline, sertraline, citalopram, and paroxetine.
- E 27. The patient has, according to World Health Organization Grading, a cortical cataract > one-quarter of the lens circumference (Grade cortical cataract-2) or a posterior subcapsular cataract >2 mm (Grade posterior subcapsular cataract-2). Patients with nuclear cataracts will not be excluded.
- E 28. The patient is currently receiving potentially cataractogenic medications, including a chronic regimen (more frequently than every 2 weeks) of any dose or route of corticosteroids or any medication that may cause cataract or worsen the vision of patients with cataract (eg, glaucoma medications) according to the Prescribing Information.
- E 29. If female, pregnant (defined as positive beta-human chorionic gonadotropin [β -HCG] blood test) or lactating or breast-feeding.
- E 30. A marked baseline prolongation of QT/QTc interval on screening electrocardiogram (ECG) (such as a QTc interval >450 msec in male subjects and >470 msec in female subjects).

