10.1.2.9 Visit 9: Week 52 (±14 days)

Visit 9 will be the last study visit of the blinded treatment period in Part 2.

Before dosing, the following assessments will be performed as listed in the study flow chart, [Section 1.3.2](#), which must be done in the following order:

- Whenever possible, the following scales and questionnaires should be done prior to clinical interaction with the Investigator:
 - BDI-II ([Appendix L](#))
 - PGIC ([Appendix N](#))
 - CGI ([Appendix M](#))
 - PDQ-39 ([Appendix O](#))
 - EQ-5D ([Appendix P](#))

- HRPQ ([Appendix R](#))
- FES ([Appendix Q](#))
- MDS-UPDRS, including H&Y ([Appendix F](#))
- PD-CRS ([Appendix G](#))
- Other questionnaires and scales
 - MoCA ([Appendix I](#))
 - Oral SDMT ([Appendix J](#))
 - TMT-A; TMT-B ([Appendix K](#))
- Review concomitant medications
- Physical examination
- General neurological examination
- Record of body weight measurement
- Vital signs (orthostatic): systolic and diastolic blood pressure (mm Hg), heart rate (bpm), respiratory rate (breaths/minute), and temperature (°C)
- 12-lead ECG
- Laboratory assessments (to be performed by the central laboratory):
 - Hematology: CBC, with differential and platelet count; coagulation profile: PT, PTT, and INR
 - Biochemistry: Sodium, potassium, chloride, calcium, ALT, AST, GGT, ALP, total and conjugated bilirubin, urea, serum creatinine, glucose, albumin, total proteins
- Urinalysis (dipstick) including glucose, protein, bilirubin, urobilinogen, pH, specific gravity, blood, ketones, nitrite, and leucocytes. Central urinalysis will be performed if any abnormality is observed in the urinalysis dipstick test.
- Urine pregnancy test (for WOCBP)
- Review of current medical conditions, with AE/SAE reporting (if any)
- Blood sampling for biomarker analyses, GCase activity and PK (as listed in study flow chart [Section 1.4.2](#))
- Pharmacogenetics DNA sample (optional; not applicable in Israel [[Appendix T](#)])
- Evaluate patients for eligibility (inclusion/exclusion criteria as listed in [Section 7.1](#), [Section 7.2](#), and [Section 10.1.2.10](#)) to transition to LTFU and receive GZ/SAR402671 treatment
- Full ophthalmology examination and photography (must be performed after the neurological examination)
- DAT scan

- Lumbar puncture for collection of CSF for PK (as listed in study flow chart [Section 1.4.2](#)) and biomarker analyses

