- Dispense IMP (the results for all Week 52 assessments, required to check inclusion/exclusion criteria, must be received and reviewed before the Week 52 visit is registered in IVRS for Week 52 IMP dispensation)

Remind patient to return to the clinic for next visit, bring their diary and any remaining capsules, if patient is enrolled in the LTFU period.

Remind patient to not take the dose at home on the clinic visiting day, the IMP will be taken at clinic.

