- Review of current medical conditions, with AE/SAE reporting (if any) (every 3 months [13 weeks] for Japanese patients only)
- Dispense IMP

At Visit 11/Week 104, Visit 13/Week 156, and Visit 15/Week 208 (ie, yearly), the following additional assessments will be performed, as listed in the study flow chart, [Section 1.3.3](#):

- Blood sampling for biomarker analysis
- Physical examination and record of body weight measurement
- 12-lead ECG
- Laboratory assessments (to be performed by the central laboratory):
 - Hematology: CBC, with differential and platelet count; coagulation profile: PT, PTT, and INR
 - Biochemistry: Sodium, potassium, chloride, calcium, ALT, AST, GGT, ALP, total and conjugated bilirubin, urea, serum creatinine, glucose, albumin, total proteins
- Urinalysis (dipstick) including glucose, protein, bilirubin, urobilinogen, pH, specific gravity, blood, ketones, nitrite, and leucocytes. Central urinalysis will be performed if any abnormality is observed in the urinalysis dipstick test.
- DAT scan
- Dispense IMP (except Visit 15/Week 208)
- Retrieve patient diary (at Visit 15/Week 208, only for patients who will transition to a long-term study with GZ/SAR402671).

Remind patient to return to the clinic for next visit.

Remind patient to not take the dose at home on the clinic visiting day, the IMP will be taken at clinic.

At Visit 15 (Week 208), patients will receive their last dose of GZ/SAR402671 at the clinic.

Visit 15 (Week 208) will be the last study visit for patients who will transition to a long-term study with GZ/SAR402671.

10.1.2.11 Eight-week follow-up visit (Period 4, end-of-study visit, Visit 16: Week 216 ±14 days)

This will be the last study visit. Patients who prematurely and permanently discontinue study medication should complete an end of treatment assessment visit (similar to Week 52/end of treatment visit for Period 2, Part 2) followed by a 8-week post-treatment follow-up visit (Visit 16). The following assessments will be performed as listed in the study flow chart, [Section 1.3.3](#), which should be done in the following order:

- BDI-II (Appendix L)
- MDS-UPDRS, including H&Y ([Appendix F](#))
- Review of concomitant medications
- Physical examination
- General neurological examination
- Visual acuity check, slit lamp examination, and fundoscopy without pupil dilation
- Vital signs: systolic and diastolic blood pressure (mm Hg), heart rate (bpm), respiratory rate (breaths/minute), and temperature (°C)

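### Placebo patients who switch to GZ/SAR402671 after Week 52 have no scheduled on-drug ALT or bilirubin until Week 104, although every patient attends the site at Week 78

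*Protocol*

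**What the plan says.** - **Switch.** Protocol 6.5: "Patients in the placebo arm will be switched to GZ/SAR402671 treatment after completing the Week 52 study visit".
- **Week 52 bloods come first.** Protocol 10.1.2.9 opens the visit with "Before dosing, the following assessments will be performed as listed in the study flow chart", and biochemistry is on that list.
- **Week 52 is also an entry check.** Footnote b of flow chart 1.3.2: "This visit will serve as the screening for patients enrolling into Period 3". Exclusion criterion E 22 (7.2.3) covers ALT/AST "or total bilirubin >2 times the upper limit of normal (ULN) at the time of screening". Under 10.1.2.9, "the results for all Week 52 assessments, required to check inclusion/exclusion criteria, must be received and reviewed before the Week 52 visit is registered" for dispensing.
- **Period 3 laboratory schedule.** Protocol 10.1.2.10: "At Visit 11/Week 104, Visit 13/Week 156, and Visit 15/Week 208 (ie, yearly), the following additional assessments will be performed". The list that follows contains the biochemistry panel with ALT, AST, GGT, ALP and bilirubin. In flow chart 1.3.3 the row "Biochemistry, urinalysis" is marked at Weeks 104, 156 and 208 only.
- **Period 3 visits.** All patients attend at Weeks 78, 104, 130, 156, 182 and 208. Japanese patients also attend at Weeks 65, 91, 117, 143, 169 and 195. Week 78 has rating scales, neurological and eye examinations, vital signs, a urine pregnancy test, adverse event review and drug dispensing, but no blood test. The extra Japanese visits have vital signs, medication review and adverse event review.
- **Liver risk.** Section 4.2.2 concludes that "there seems to be no safety concern in humans involving the gastrointestinal tract and the liver". Section 10.6.1 reports raised liver tests in a 4-week rat study and relies on the clinical laboratory tests for close liver monitoring. It stands under a lead-in in 10.6 that calls such risks theoretical and common to the drug class. An ALT increase is an adverse event of special interest, reportable within 24 hours (10.4.1.3, 10.4.4). Section 10.3.3 lists confirmed ALT and bilirubin thresholds among reasons that may justify stopping treatment.

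**The concern.** The year of first exposure gets very different laboratory cover depending on when it falls. A patient randomized to drug is tested within two weeks and repeatedly afterwards. A placebo patient who starts the same drug at Week 52 is tested once, at the end of the year. The Week 52 result shows that the patient is fit to start, but it is an off-drug value.

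The ALT reporting rule and the liver reason for stopping both need a laboratory result to act on. In a switched patient without symptoms, nothing in the schedule provides one during the first year on drug. A value would appear earlier only through an unscheduled test prompted by an adverse event, an end-of-treatment visit of the Week 52 type, or local tests when Covid-19 delays a visit. None of these is planned for a continuing, symptomless patient.

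**Working it through.** There is no sample-size or power figure to reproduce; the check is of the visit calendar.

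**Inputs**
- Biochemistry in Period 2 (flow chart 1.3.2): screening, Day 1, Weeks 2, 4, 13, 26, 39, 52. The Week 4 visit text (10.1.2.5) lists no laboratory tests. With or without Week 4, the first on-drug draw is at Week 2 and the longest nominal gap is 13 weeks.
- Biochemistry in Period 3 (flow chart 1.3.3 and 10.1.2.10): Weeks 104, 156, 208.
- Windows (10.1.2): Weeks 2 to 39 ±3 days; Week 52 ±14 days (Weeks 50 to 54); later Period 3 visits ±7 days.
- Planned numbers (11.1): 108 per arm, 216 in total, about 10% early terminations or unevaluable.

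**Time from switch to first scheduled on-drug liver test, as planned**
- Nominal: 104 − 52 = 52 weeks.
- Shortest: 103 − 54 = 49 weeks. Longest: 105 − 50 = 55 weeks.

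**Comparison with patients randomized to drug**
- First on-drug panel: Week 2.
- On-drug panels in the first 52 weeks: six (Weeks 2, 4, 13, 26, 39, 52), or five without Week 4. A switched patient has one.
- Longest nominal gap in Period 2: 13 weeks. With windows, Week 39 to Week 52 can reach 13 weeks + 3 + 14 days = 15.4 weeks.
- From Week 52 on, the gaps are 104 − 52, 156 − 104 and 208 − 156, each 52 weeks, in both arms.

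**With a liver panel added at Week 78**
- Nominal: 78 − 52 = 26 weeks. Range: 77 − 54 = 23 to 79 − 50 = 29 weeks.

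**With a panel also at Week 65 (Japanese patients)**
- Nominal: 65 − 52 = 13 weeks. Range: 64 − 54 = 10 to 66 − 50 = 16 weeks.

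**What the addition leaves alone**
- Week 104 to 156 and Week 156 to 208 stay at 52 weeks.

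**Numbers affected**
- Switched patients: 108 × 0.9 = 97.2, about 97 at most.
- Samples at Week 78: 216 × 0.9 = 194.4, about 194 at most.
- If all 27 Part 1 patients also entered Part 2: 243 × 0.9 = 218.7, about 219.

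The Covid-19 extension of up to 3 months (10.1.2) is left out; it can move these intervals in either direction.

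**The case against.** The strongest reply is that the schedule is proportionate to the stated risk. Section 4.2.2 sees no human liver concern and 10.6 treats liver effects as a theoretical class risk. The lens is the organ singled out for close monitoring in 4.2.2, and Week 78 does include an eye examination. Liver values are reviewed before drug is dispensed at Week 52. An independent monitoring committee follows safety throughout (6.4.1), and the first-step analysis (11.5.2) will supply on-drug ALT data from the randomized arm. All of this stands and keeps the point minor. None of it gives a scheduled on-drug value in a switched patient: a committee can review only what has been drawn, and group data from the other arm do not protect an individual at first exposure.

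A second reply is that 26 weeks is still late compared with Week 2. That is fair. The proposal uses visits that already exist and does not claim to match Period 2.

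A third is timing. This version is dated 09 February 2021, and the amendment history places the 52-week analysis in the first quarter of 2021. That analysis needs Week 52 data from all Part 2 patients. By inference, nearly all had reached Week 52 and many had passed Week 78. This limits how many patients the change can reach.

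Readers might also infer more than the documents support:
- *That flow chart and text conflict.* For Period 3 they agree; this is a design choice.
- *That drug-arm patients are tested at least every 13 weeks throughout.* This holds in Period 2 only.
- *That a Week 78 panel ends year-long gaps.* It shortens the first on-drug interval only.
- *That the recheck before permanent discontinuation in 10.3.3 contradicts the 72-hour retest footnote in Appendix S.* The ALT diagram to which the footnote belongs is not shown, and 10.3.3 can be read as verifying a result rather than redrawing blood.

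**Conclusion.** The point holds as an optional safety improvement. A switched placebo patient goes about 52 weeks on GZ/SAR402671 (49 to 55 within the ordinary windows) before the first scheduled ALT or bilirubin, while all patients attend the site halfway through that interval without a blood test.

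The interval is counted from the Week 52 visit. Because dispensing waits for results, the first active dose may come slightly later, so actual time on drug may be a little shorter. The figure of about 97 patients assumes that the planned 10% loss applies equally to the placebo arm. It is an upper limit, because the Week 52 eligibility check may exclude some patients and others are already past Week 78. The documents give no evidence of liver harm in humans, and the point does not depend on any.

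**What to change.** In flow chart 1.3.3 and section 10.1.2.10, add a liver panel (ALT, AST, ALP, total and conjugated bilirubin, albumin, total protein) at:

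- the existing Week 78 visit, for all Period 3 patients;
- the existing Week 65 visit, for Japanese patients.

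Draw it in both original arms. Testing only switched patients would reveal the Period 2 allocation, which 6.5 keeps blinded during follow-up.

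**Cost.** No new visit. One extra blood draw per patient, or two for Japanese patients. At Week 78 this is at most about 194 samples for the 216 planned patients (about 219 if all Part 1 patients also take part). The number of Japanese patients in Part 2 is not given, so the Week 65 total cannot be stated. If a Covid-19 delay makes Week 52 overlap Week 65, section 10.1.2 records Week 65 as missed, and that patient's first on-drug panel falls at Week 78.
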